## BACKGROUND

Antimicrobial stewardship programs (ASPs) often restrict their activities to inpatient antimicrobial-prescribing. However, at least 40% of all antimicrobial exposure associated with an acute-care hospital stay is prescribed at the time of hospital discharge (i.e., post-discharge). Post-discharge antimicrobials mediate clinical outcomes after discharge and may facilitate the spread of antimicrobial resistance.

Several studies have shown that post-discharge antimicrobial use is often inappropriate. We used national data to show that 61% of fluoroquinolone treatment days were prescribed at hospital discharge; manual chart reviews at 9 hospitals found that 40% of these post-discharge fluoroquinolone prescriptions were either unnecessary or sub-optimal. Other studies have found that 53-79% of all post-discharge antimicrobials are either unnecessary or sub-optimal.

Post-discharge antimicrobials are an important target for antimicrobial stewardship. However, inpatient stewardship metrics do not capture post-discharge antimicrobials and ASPs frequently do not evaluate these prescriptions. A 2016 Veterans Health Administration (VHA) survey found that less than 50% of hospitals routinely reviewed targeted antimicrobials at discharge. According to a 2016 survey in Michigan, only 17% of 48 hospitals had a process for reviewing outpatient antimicrobial orders at discharge. Nearly all hospitals responding to these two surveys reported that they had an inpatient ASP.

We currently do not know how inpatient ASP resources can be effectively leveraged to improve post-discharge antimicrobial use. Several randomized-controlled trials have demonstrated that post-prescription audit-and-review (PPR) can reduce and improve inpatient antimicrobial use, but these studies did not measure the effect of PPR on post-discharge antimicrobial use. Two single-center non-randomized studies, including a study by our team of investigators, showed that inpatient PPR can decrease and improve post-discharge antimicrobial use. However, these findings may not be generalizable to other settings.

If the goal is to improve post-discharge antimicrobial use, a potentially effective strategy may be a PPR process focused solely on prescriptions for patients who will soon be discharged. However, such a PPR intervention would require an innovative approach, as ASPs typically do not know when patients will be discharged.

## METHODS

### Trial design:

We will perform a stepped-wedge cluster-randomized trial to assess the effectiveness of discharge- post-prescription audit-and-review (i.e. discharge-PPR) in safely reducing post-discharge antimicrobial use.

There are ten sites taking part in this study. Based on the stepped wedge study design, randomization will be performed at the site-level with all eligible patients having access to the intervention once a site has entered the intervention phase. Each facility will begin in control status with one facility crossing into the intervention every two weeks following a 24-week baseline period. A simple randomization scheme using a random number generator will be used a priori to determine the order of implementation. Once clinical rollout is complete, all sites will continue to perform the intervention for another 2.5-3 months. No site will perform the intervention for longer than 6 months.

**Participants:** We will enroll up to 9 antimicrobial stewardship teams and their respective hospital sites (n=10). Note that one stewardship team covers two hospitals.

Inclusion criteria: An acute-care hospital with an antimicrobial stewardship team

Exclusion criteria: A discharge-focused PPR process is already in place or will be implemented soon

Method of recruitment: We will recruit sites through the EpiCenter's national conference calls and known professional contacts of the study PI.

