### **Interventions:**

**Pre-intervention activities:** All sites must identify a site principal investigator (PI), i.e. a physician who preferably has experience with antimicrobial stewardship. Each site must also identify a study pharmacist. Ideally, the study pharmacist will already be part of stewardship activities.

- *Baseline survey of ASP activities:* All participating hospitals will complete an electronic survey about their baseline ASP activities.
- *Process development:* Before the intervention, the pharmacist and site PI will develop a process for identifying eligible patients for discharge-PPR audits; this process may include using information technology tools and collaborating with case managers or discharge coordinators.
- *Collaborative learning calls:* Nine months before the intervention begins, the study coordinator will start organizing collaborative learning calls for the study PI ([name]) and the study personnel (site PI and pharmacist) at all participating sites. During these monthly calls, sites will share their experience developing a process to identify patients who will be discharged within 48 hours. In addition, participants will review the audit-and-feedback literature and their own personal experience with stewardship to facilitate discussion about the optimal approach to discharge-PPR .

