### **Intervention activities:**

During the intervention, a study team member (either a physician or pharmacist) will perform discharge-PPR every weekday for patients on select medical services who are receiving an antimicrobial and whose discharge is anticipated within the next 48 hours. The number of services selected for PPR will be aimed at providing approximately 200 discharges per month per facility.

The site PI will provide physician-support for these PPR activities. Discharge-PPR audits will focus on optimizing antimicrobial selection, dose, and duration before discharge. The pharmacist will communicate all recommendations resulting from the audit to the primary prescribers. Site PIs and pharmacists will also participate in the collaborative learning calls every month during their sites' intervention periods.

All hospitals may continue their usual stewardship activities during the trial. However, hospitals will be strongly encouraged to not start any other new stewardship interventions targeting antimicrobial-prescribing at discharge.

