### **Further description of discharge-PPR process:**

- Content: Real-time feedback on the selection, dose, and duration of antimicrobials prescribed at hospital discharge

- Delivery method: Feedback will be preferably delivered in-person or by telephone. Electronic, asynchronous communication may also be used.
- Unit of delivery: The feedback will be given to an inpatient provider directly caring for the patient who is receiving antimicrobials.
- Deliverer: Feedback will be delivered by the participating stewardship teams or involved extenders.
- Setting: The intervention will be delivered on the acute-care hospital units before patients receiving antimicrobials are discharged.
- Exposure quantity and duration: Feedback will be given during weekday working hours.
- Time span: 2-6 months, depending on when a site is randomized to the intervention
- Activities to increase compliance or adherence: Baseline education about duration of antimicrobial therapy for common infections treated in hospitalized patients.

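### Does the stewardship team shared by two separately randomised hospitals call for a prespecified check on contaminated control periods?

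*Combined protocol and SAP*

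**What the plan says.** Under Trial design, "randomization will be performed at the site-level", with "one facility crossing into the intervention every two weeks" after a 24-week baseline. The order comes from simple randomisation, with no constraint tied to teams. Up to nine teams take part with ten hospitals, and the plan states openly: "Note that one stewardship team covers two hospitals".

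On delivery, the further description of the discharge-PPR process says: "Feedback will be delivered by the participating stewardship teams or involved extenders". The pre-intervention activities require a principal investigator for every site and add: "Each site must also identify a study pharmacist". They do not say that these must be different people at the two hospitals.

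Three provisions bear on the control condition in general. A hospital is excluded if "A discharge-focused PPR process is already in place or will be implemented soon". Under Intervention activities, "hospitals will be strongly encouraged to not start any other new stewardship interventions targeting antimicrobial-prescribing at discharge". Usual stewardship may continue throughout. None of these addresses a shared team.

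The Statistical Methods paragraph gives one model: fixed effects for time step and intervention status, a random site intercept, and covariates. It has no team term and names no sensitivity analysis.

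**The concern.** A stepped wedge compares hospitals that have crossed with hospitals that have not. With one crossing per step, the two hospitals under one team cannot cross together, so there is always a window in which that team's first hospital is in intervention and its second is analysed as control. Staff who audit selection, dose and duration at the first could apply the same habits at the second. Its last control blocks would then carry part of the effect, and the estimate would be pulled toward zero. If the team were instead stretched and gave less usual stewardship at the second hospital, the estimate would move the other way. At stake is the size of the reported reduction in post-discharge length of therapy (LOT). A reader could not tell from the primary model alone whether this had happened.

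**Working it through.** **Inputs.** Sample Size section: 10 sites; 24 two-week periods; first crossover in period 13, then one site per step; effect 10% of 135 = 13.5 LOT per 100 admissions; intra-cluster correlation (ICC) 0.75; cluster-level SD 3.4; 100 discharges per site per period; type I error 5% (taken as two-sided). Assumption: a fraction c of the effect reaches the later hospital in the blocks between the two crossovers. The documents give no value for c.

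**1. The plan's power.** For a random site intercept (variance τ²), residual variance σ² of a site-period rate, I sites and T periods:

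Var = Iσ²(σ² + Tτ²) / [(IU − W)σ² + (U² + ITU − TW − IV)τ²]

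The schedule gives U = 75 intervention site-periods, W = 585 (sum of squared period totals) and V = 645 (sum of squared site totals). Reading 3.4 as the between-site SD, τ² = 11.56 and σ² = 11.56 × 0.25/0.75 = 3.853.

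- Numerator: 10 × 3.853 × (3.853 + 24 × 11.56) ≈ 10,839.
- Denominator: 165 × 3.853 + 3,135 × 11.56 ≈ 36,876.
- SE = √0.294 = 0.54. Reading 3.4 as the total SD of the rate gives 0.47.

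13.5/0.54 is about 25 SEs, so the stated power above 90% is reproduced.

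**2. Length of the overlap.** There are 45 placements of the pair. Gaps of 1 to 9 steps occur 9, 8, 7, 6, 5, 4, 3, 2 and 1 times. The mean is 165/45 = 3.67 steps (7.3 weeks) and the median 3 steps (6 weeks). The affected blocks average 3.67 of 165 control site-periods, or 2.2%.

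**3. Effect on the estimate.** The generalised least-squares estimate is a weighted sum of the site-period rates. Its expectation is 13.5 × (1 + c × S), where S is the summed (negative) weight of the affected blocks. Over all 45 placements:

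| c | Mean ratio to truth | Worst order | Mean loss (LOT per 100) | Mean loss / SE of 0.54 |
|---|---|---|---|---|
| 0.25 | 0.972 | 0.944 | 0.375 | 0.7 |
| 0.5 | 0.944 | 0.889 | 0.75 | 1.4 |
| 1 | 0.889 | 0.777 | 1.5 | 2.8 |

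In the worst case, 13.5 × 0.777 = 10.5 is still more than 19 SEs. With c = −0.25 the mean ratio is 1.028.

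**4. What a check would show.** Refitting without the affected blocks removes this bias by construction and raises the SE by 3.9% on average (9.8% at most). On the plan's inputs, the SE of the difference between the two fits averages 0.12 to 0.14, so c = 0.25 would show as a shift of about 2.5 to 2.8 such SEs.

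That sensitivity depends on a residual SD of only √3.853 = 1.96 for a rate of 135 per 100 discharges. If counts had Poisson noise (an assumption), the residual SD would be √135 = 11.6. At ICC 0.75 the primary SE becomes 0.542 × √(135/3.853) = 3.2. The mean losses at c = 0.25 and 0.5 are then 0.375/3.2 = 0.12 and 0.75/3.2 = 0.23 of an SE. The SE of the difference averages 0.85, and the refit moves by about 0.4, 0.8 and 1.7 of those SEs at c = 0.25, 0.5 and 1. Days from one prescription come together, so the real noise may be larger and the check weaker still.

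**The case for a change.** The strongest case for a change is that the overlap is certain, with only its length left to chance, and no existing safeguard covers it. On the plan's own SE, half carry-over biases the estimate by 1.4 SEs, enough to displace a confidence interval. The remedy is a sentence on staffing and one extra fit, and naming the fit in advance would prevent selective reporting.

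The facts and the arithmetic stand. The mechanism and the gain are weaker.

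- Discharge-PPR is an active weekday audit of identified patients on chosen services, with feedback to the provider caring for that patient. Prescribers at the later hospital receive none until it crosses. Full carry-over would amount to starting there early, which is a departure from the schedule rather than passive spillover.
- Each site names its own pharmacist, and extenders may deliver the feedback, so the shared team need not do the work at both hospitals. Nothing in the documents supports the stretched-team mechanism.
- This is not the only route by which control sites meet the intervention. The monthly learning calls begin nine months before it and bring together study staff from all sites to discuss how best to run the audits. A refit without one hospital's blocks cannot detect that exposure.
- Selective reporting has little room here, because the affected blocks follow mechanically from the drawn order and the two-weekly data.

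**Conclusion.** No change is needed. The shared team is a disclosed feature of a trial that the plan itself calls a pilot, and any carry-over is a possibility, not a documented fact. At an assumed quarter to half carry-over, the mean attenuation is 3% to 6% (6% to 11% in the worst order).

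If the plan's SD of 3.4 is right, the effect is about 25 SEs and a loss of that size leaves the conclusion intact. If the residual noise is nearer Poisson, the bias is 0.12 to 0.23 of an SE on average and the proposed check could hardly tell it from chance. In neither case would the extra fit alter what the trial concludes.

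Redesign offers nothing better. Placing the pair on consecutive steps would raise the primary SE by about 1.4% to 3.4%, at assumed period-level correlations between the two hospitals of 0.2 to 0.5, and would have one team launch two hospitals two weeks apart. A line in the final report on whether the two hospitals shared delivery staff, with the refit if they did, is ordinary good practice and needs no amendment.

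This rests on the schedule as written, a constant treatment effect as the plan assumes, and the assumed carry-over fractions.

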### **Interventions:**

**Pre-intervention activities:** All sites must identify a site principal investigator (PI), i.e. a physician who preferably has experience with antimicrobial stewardship. Each site must also identify a study pharmacist. Ideally, the study pharmacist will already be part of stewardship activities.

- *Baseline survey of ASP activities:* All participating hospitals will complete an electronic survey about their baseline ASP activities.
- *Process development:* Before the intervention, the pharmacist and site PI will develop a process for identifying eligible patients for discharge-PPR audits; this process may include using information technology tools and collaborating with case managers or discharge coordinators.
- *Collaborative learning calls:* Nine months before the intervention begins, the study coordinator will start organizing collaborative learning calls for the study PI ([name]) and the study personnel (site PI and pharmacist) at all participating sites. During these monthly calls, sites will share their experience developing a process to identify patients who will be discharged within 48 hours. In addition, participants will review the audit-and-feedback literature and their own personal experience with stewardship to facilitate discussion about the optimal approach to discharge-PPR .

### **Intervention activities:**

During the intervention, a study team member (either a physician or pharmacist) will perform discharge-PPR every weekday for patients on select medical services who are receiving an antimicrobial and whose discharge is anticipated within the next 48 hours. The number of services selected for PPR will be aimed at providing approximately 200 discharges per month per facility.

The site PI will provide physician-support for these PPR activities. Discharge-PPR audits will focus on optimizing antimicrobial selection, dose, and duration before discharge. The pharmacist will communicate all recommendations resulting from the audit to the primary prescribers. Site PIs and pharmacists will also participate in the collaborative learning calls every month during their sites' intervention periods.

All hospitals may continue their usual stewardship activities during the trial. However, hospitals will be strongly encouraged to not start any other new stewardship interventions targeting antimicrobial-prescribing at discharge.

### **Further description of discharge-PPR process:**

- Content: Real-time feedback on the selection, dose, and duration of antimicrobials prescribed at hospital discharge

- Delivery method: Feedback will be preferably delivered in-person or by telephone. Electronic, asynchronous communication may also be used.
- Unit of delivery: The feedback will be given to an inpatient provider directly caring for the patient who is receiving antimicrobials.
- Deliverer: Feedback will be delivered by the participating stewardship teams or involved extenders.
- Setting: The intervention will be delivered on the acute-care hospital units before patients receiving antimicrobials are discharged.
- Exposure quantity and duration: Feedback will be given during weekday working hours.
- Time span: 2-6 months, depending on when a site is randomized to the intervention
- Activities to increase compliance or adherence: Baseline education about duration of antimicrobial therapy for common infections treated in hospitalized patients.

### **Objectives:**

AIM 1: Evaluate whether discharge post-prescription audit-and-review (PPR) can safely reduce post-discharge antimicrobial use across participating hospitals.

Hypothesis 1: The discharge audit-and-feedback intervention will reduce post-discharge antimicrobial use without adversely affecting patient safety.

AIM 2: Through monthly collaborative learning calls with participating sites, determine barriers and facilitators encountered by antimicrobial stewardship teams in their implementation of the discharge-PPR process.

### **Outcomes:**

We will use the RE-AIM framework (page 6) to assess our pilot trial. Clinical outcomes are listed below. Data for all clinical outcomes will be extracted from the respective data systems of each participating site. All data will be submitted to the project PI for final data analysis.

#### **Primary outcome**

The primary outcome will be post-discharge antimicrobial length of therapy (LOT) per 100 admissions. This outcome will be collected every two weeks during the study period for all services or wards participating in the project.

#### **Secondary outcomes**

Additional outcomes will include inpatient antimicrobial use (inpatient LOT per 100 admissions), length of stay, and 30-day hospital re-admission rates. These secondary outcomes will only be measured for patients who were discharged from a participating service or ward.

*Process measures:* Each day, the study pharmacist will record the number of patients audited during discharge-PPR, the number of PPR recommendations communicated to providers, and the number of recommendations that were accepted.

*Implementation outcomes:* We will use the RE-AIM framework to assess our intervention. Feasibility will be evaluated on 2 domains: 1) the development of a local process to identify patients who are on antimicrobials within 48 hours of hospital discharge, and 2) the initiation of the discharge-PPR intervention. To further understand the implementation process, the study coordinator will take notes during the collaborative learning calls. We will also record these calls. We will perform a rapid template analysis to describe each site's implementation process, including barriers and facilitators to successful implementation. Through a weekly survey, we will also assess each site's fidelity to the discharge-PPR process and the cost (i.e. time) of the intervention. Through a post-intervention electronic survey, we will assess the acceptability of discharge-PPR to frontline prescribers.

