### Applying the RE-AIM implementation framework to our evaluation of this pilot study's findings

Dimension	Definition 	Measurement
Reach	
The absolute number, proportion and representativeness of individuals who are willing to participate in a given initiative or program, and reasons why they do or do not participate
 
Who actually participates or is exposed to the initiative?
	
Monitor the number of prescribers at each site who receive feedback.

Effectiveness	
The effect of an intervention on important individual outcomes, such as clinical events, quality of life, and economic outcomes
	
See primary and secondary outcomes, as listed above

Adoption	
The absolute number, proportion and representativeness of settings and agents who are willing to start a program and why they are willing to start it
 
Where is the program applied and who applied it?
	
Describe the location and complexity of the intervention sites. During the introductory call, ask the teams at the intervention sites why they want to participate.

Implementation	
Fidelity to the key elements of an evidence-base practice, including consistency of delivery as intended and the time and cost of the program
 
How consistently was the program delivered? How was it adapted to each setting? How much did it cost? Why did it achieve the observed result?
	
Measure fidelity by tracking the number of audits performed and recommendations made.
 
Measure acceptability with a post-intervention survey of frontline prescribers.
 
Measure implementation cost by having the project team track the time committed to project activities on a weekly basis.

Maintenance	
The extent to which a program or policy becomes institutionalized or part of the routine organizational practices and policies.
 
How long are the results of the program or policy sustained?
	
Assess whether sites are still performing discharge audit-and-feedback 6 months after the project ends

1. All definitions are taken from <https://www.re-aim.org>

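### Death after discharge is not an outcome, so 30-day re-admission alone cannot support the safety half of Hypothesis 1

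*Combined protocol and SAP*

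**What the plan says.** Under Objectives, Hypothesis 1 states that the intervention "will reduce post-discharge antimicrobial use without adversely affecting patient safety". Under Intervention activities, "Discharge-PPR audits will focus on optimizing antimicrobial selection, dose, and duration before discharge", so any harm from under-treatment would arise largely after the patient has left hospital.

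Secondary outcomes reads: "Additional outcomes will include inpatient antimicrobial use (inpatient LOT per 100 admissions), length of stay, and 30-day hospital re-admission rates". The population follows: "These secondary outcomes will only be measured for patients who were discharged from a participating service or ward". The section gives no numerator, denominator or handling of death for "30-day hospital re-admission rates".

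Under Outcomes, "Data for all clinical outcomes will be extracted from the respective data systems of each participating site"; no vital-status source is named. In the RE-AIM table, the Effectiveness row says only "See primary and secondary outcomes, as listed above" and adds no safety measure. Statistical Methods describes a model for the primary outcome alone.

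**The concern.** Safety is half of what Hypothesis 1 claims. Inpatient length of therapy and length of stay describe the hospital stay, which leaves re-admission as the only listed outcome that could show harm after discharge. A patient who dies at home on day 10 can no longer be re-admitted. In a simple proportion of discharged patients, that person sits in the denominator and not in the numerator, exactly like a patient who recovered. The most serious consequence of under-treatment would therefore not count against the intervention. The risk is that an unchanged re-admission rate is read as evidence of safety when it is silent on such deaths.

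**Working it through.** The plan states no figure for re-admission, death or any safety comparison. Its power statement (more than 90%, Sample Size) concerns the primary outcome and does not bear on this point. The check is therefore on what the re-admission rate can show, using assumed values.

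**1. The rate written out.** Let r be baseline 30-day re-admission, y the extra deaths without re-admission, q the share of those patients who would otherwise have been re-admitted, and x the extra re-admissions caused by harm. All are per 100 discharges except q, which is a proportion. Then:

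- re-admission = r − y·q + x
- re-admission or death, change from baseline = x + y·(1 − q)
- death alone, change from baseline = y

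In the first line y enters only through −y·q, which is zero or negative. Whatever the values, such deaths never raise the re-admission rate.

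**2. Illustration** (assumed r = 15%, y = 1 point, x = 0; the composite starts from 15%, leaving aside baseline deaths):

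| q | Re-admission | Re-admission or death | Death alone |
|---|---|---|---|
| 0.15 | 15 − 0.15 = 14.85% | 14.85 + 1 = 15.85% | +1 point |
| 0.50 | 15 − 0.50 = 14.5% | 14.5 + 1 = 15.5% | +1 point |
| 1.00 | 15 − 1.00 = 14.0% | 14.0 + 1 = 15.0% | +1 point |

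The last row shows why death is needed separately: at q = 1 the composite does not move either.

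**3. Range.** With r = 10–20%, y = 0.5–2 points, q from r to 1 and x = 0, the fall runs from 0.5 × 0.10 = 0.05 points to 2 × 1 = 2.0 points. For a smaller y of 0.1 point and q of 0.15–0.30, it is 0.015–0.03 points.

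**4. When the rate actually falls.** Only if x < y·q. At y = 1 and q = 0.15, extra re-admissions of 0.15 points cancel the fall; at q = 1 it takes 1.0 point.

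**5. Scale.** The Sample Size layout (24 two-week blocks, 12 of them baseline, one site crossing per block) gives 12 + 11 + … + 3 = 75 intervention site-blocks. At 100 discharges each, that is 7,500 discharges. A rise of 1 point is 75 deaths, 0.2 point is 15, and 0.1 point is 7.5.

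**6. Precision of the re-admission comparison.** The Hussey–Hughes variance for this layout is I·σ²(σ² + T·τ²) / [(I·U − W)σ² + (U² + I·T·U − T·W − I·V)τ²], with I = 10, T = 24, U = 75, W = 585 and V = 645. The bracketed coefficients are 750 − 585 = 165 and 5,625 + 18,000 − 14,040 − 6,450 = 3,135. Take σ² = r(1 − r)/100.

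- r = 10%, between-site SD τ = 0: variance = 10 × 0.0009 / 165, SE = 0.74 points.
- r = 20%, τ = 5 points: variance = 10 × 0.0016 × 0.0616 / (0.264 + 7.8375), SE = 1.10 points.

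A shift of 0.15–0.30 points (y = 1, q = 0.15–0.30) is then 0.15/1.10 = 0.14 to 0.30/0.74 = 0.41 standard errors.

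**The case against.** A reader might infer that the protocol scores a death as a good outcome. It does not say so. It names a re-admission rate and is silent on death, and it never labels re-admission as the safety outcome or sets a safety decision rule. Both readings follow from the list of outcomes and the missing rule, and should be put that way.

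A reader might also infer that harm would show up as benefit. That holds only when x < y·q. Under-treatment may well bring patients back to hospital, and those who die after a re-admission within 30 days still count as events. Even when the condition is met, a shift of 0.14–0.41 standard errors would look like no change rather than improvement.

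The 1-point death rise is an extreme assumption. The planned effect is 10% of 135, or 0.135 day per admission. Treating admissions as discharges, 7,500 of them give about 1,012 days avoided, so 75 deaths would be one per 13.5 days. The denominator also includes patients who were never audited.

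Finally, the sites' own systems may hold few out-of-hospital deaths, and even constant under-capture shrinks an absolute difference. If the share captured is c, a rise of y reads as c·y. The protocol also calls itself a pilot.

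All of this stands as a limit on size and wording. None of it supplies an outcome that would register a death without re-admission. Incomplete capture attenuates the signal; leaving death out removes it altogether.

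**Conclusion.** The point holds as a gap in the safety assessment. Deaths without re-admission are either unseen or counted as not re-admitted, so a flat or lower re-admission rate cannot on its own support the safety half of Hypothesis 1. That conclusion needs no assumed numbers. It rests on the list of outcomes, on the absence of any rule for death, and on reading the rate as a simple proportion of discharged patients.

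The size cannot be estimated from the documents, which give no re-admission rate, death rate or overlap between the two. The figures above are illustrations over assumed ranges. They do not show that harm is likely, or that re-admissions would fall if it occurred.

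**What to change.** Under Secondary outcomes, add all-cause death within 30 days of discharge, taken from the same site data systems. Report three measures by control and intervention period: re-admission, death, and re-admission or death, whichever comes first. Where a difference is estimated, adjust for step as in the primary model, because the two conditions differ in calendar time.

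Record each site's source for deaths and keep it unchanged across periods. State in the conclusion that out-of-hospital deaths are likely to be under-counted at some sites and that this attenuates any difference towards no harm.

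The cost is one more extracted field (vital status with date) in an extraction already planned, subject to what each of the ten sites' systems holds. The intervention, randomization, primary outcome and its power are unchanged.
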